8.2.2 Primary analysis of the primary efficacy endpoint

The primary endpoint is the HiSCR₅₀ response at Week 16 and corresponding analyses are based on the RS. The primary efficacy analysis will evaluate the composite estimand in the RS as described in Table 8-1. The composite estimand combines the clinically meaningful improvement from Baseline based on the HiSCR₅₀ response and completion of study treatment through Week 16 without receiving systemic antibiotic rescue medication or discontinuing IMP due to an AE or lack of efficacy.

The following 4 attributes describe the estimand that will be used to define the treatment effect of interest for the primary efficacy analysis:

1. Population=Study participants meeting the protocol-specified inclusion/exclusion criteria.
2. Study participant-level outcome=HiSCR₅₀ at Week 16.
3. Intercurrent event handling=An intercurrent event is defined as receipt of systemic antibiotic rescue medication or discontinuation of study treatment due to an AE or lack of efficacy prior to Week 16. More information is provided in Section 3.9. A composite strategy will be implemented in which a positive clinical outcome is defined as achieving HiSCR₅₀ at Week 16 and not receiving systemic antibiotic rescue medication, and not discontinuing study treatment due to an AE or lack of efficacy through Week 16. Any missing data at Week 16 that are not preceded by an intercurrent event will be imputed using multiple imputation as defined in Section 4.2.1. The rationale for this composite estimand is provided in Section 4.2.3.1.

4. Population-level summary measure=conditional odds ratio comparing bimekizumab to placebo adjusted for stratification factors used in the randomization.

The statistical hypothesis for the HiSCR₅₀ response at Week 16 is that the conditional odds ratio for the HiSCR₅₀ response in the bimekizumab treatment group relative to the placebo group is equal to 1.

The primary analysis will be based on a logistic regression model including a fixed effect for treatment, Hurley stage at Baseline, and Baseline antibiotic use. The odds ratio versus placebo, p-value (from Wald test), and 97.5% CI will be calculated. If one dose regimen is tested at the 0.05 significance level as determined in Section 4.5, then the confidence interval will be 95% instead of 97.5% for that dose with a corresponding $Z_{\alpha/2}$ of 1.96.

The number and percentage of participants who are HiSCR₅₀ responders at Week 16 will be summarized.

By-participant listings of HiSCR responder endpoints will be provided.

8.2.3 Sensitivity analyses of the primary efficacy endpoint

The following sensitivity analyses for the primary efficacy endpoint will be performed to evaluate the assumptions related to the handling of missing data. Details of the estimands for each analysis are described in Table 8-1.

8.2.3.1 Nonresponse imputation

As a sensitivity analysis, any missing data at Week 16 that are not preceded by an intercurrent event (ie, receipt of systemic antibiotic rescue medication or discontinuation of study treatment due to an AE or lack of efficacy) will be imputed as nonresponse. That is, participants who experience an intercurrent event will be imputed as nonresponder at the timepoint of the event and all subsequent timepoints (including any recorded data after the event), and all missing data will also be imputed as nonresponse.

The same analysis model as in the primary efficacy analyses will then be used on the imputed data set.

8.2.3.2 MI-MCMC / Reference-based imputation

Deviations from the missing at random pattern will be evaluated using a reference-based MI approach (see Section 4.2.2.2). Intermittent missing data will be imputed using the MCMC method. The remaining monotone missing data will be assumed to follow a missing not at random pattern. These data will be imputed using a reference-based approach in which the MI model is based on data from the placebo group, thereby assuming that monotone missing data follow a trajectory similar to the placebo group.

The same analysis model as in the primary efficacy analyses will then be used on the imputed data set.

8.2.3.3 Tipping point analysis

Tipping point analyses will be performed to evaluate missingness assumptions. Various delta adjustments will be made to the assumed responses on the monotone missing data in each treatment group independently with various degrees of plausibility. It will include scenarios where study participants who have missing data and are randomized to bimekizumab have a

lower probability of response compared to study participants who have missing data and were randomized to placebo. This includes the worst-case scenario where study participants who have missing data and are randomized to bimekizumab are considered nonresponders, while study participants who have missing data and were randomized to placebo are considered responders. The goal of the tipping point analysis is to systematically vary assumptions until there is no evidence of a treatment effect (if possible). The plausibility of such required delta adjustment will then be assessed.

Refer to Section 4.2.2 for more details on the methodology.

8.2.3.4 Treatment policy

The treatment policy strategy for addressing intercurrent events will be considered. This will be based on an analysis of all available data at Week 16 regardless of the occurrence of intercurrent events. This analysis will use the same models specified for the primary analysis, where study participants are analyzed according to their randomized treatment, even if they discontinued study treatment for any reason prior to Week 16. Even though efforts will be made to collect the primary outcome data for all study participants at Week 16, there may still be some study participants for whom Week 16 efficacy data cannot be obtained. In this case, missing data will be imputed using multiple imputation under the assumption of MAR (see Section 4.2.2). The same analysis model as in the primary efficacy analyses will then be used on the imputed data set and the resulting inferential statistics will then be combined into a single inference using Rubin's rule.

8.2.3.5 Analysis on observed cases

An additional supportive analysis will be based on observed data only for study participants with a lesion count assessment at Week 16 who have not had an intercurrent event on or before Week 16. Study participants with missing data at Week 16 will be treated as missing (see Section 4.2.2).

The same analysis model as in the primary efficacy analyses will then be used on the imputed data set.

8.2.3.6 Analysis on FAS

The primary efficacy analyses from Section 8.2.2 will be repeated based on the FAS.

8.2.3.7 Analysis on PPS

The primary efficacy analyses from Section 8.2.2 will be repeated based on the PPS.

8.2.3.8 Analysis on CFS

The primary efficacy analyses from Section 8.2.2 will be repeated based on the CFS.

8.2.3.9 Analysis including COVID-19 impact as intercurrent event

An additional sensitivity analysis will include an additional intercurrent event. The composite estimand combines the clinically meaningful improvement from Baseline based on the HiSCR₅₀ response and completion of study treatment through Week 16 without receiving systemic antibiotic rescue medication or discontinuing IMP due to an AE or lack of efficacy.

The following 4 attributes describe the estimand that will be used to define the treatment effect of interest for this sensitivity efficacy analysis:

1. Population=Study participants meeting the protocol-specified inclusion/exclusion criteria.
2. Study participant-level outcome=HiSCR₅₀ at Week 16.
3. Intercurrent event handling=An intercurrent event is defined as receipt of systemic antibiotic rescue medication, discontinuation of study treatment due to an AE or lack of efficacy prior to Week 16, or missing data due to COVID-19. More information is provided in Section 3.9. A composite strategy will be implemented in which a positive clinical outcome is defined as achieving HiSCR₅₀ at Week 16 and not receiving systemic antibiotic rescue medication, not discontinuing study treatment due to an AE or lack of efficacy through Week 16, and not having missing data due to COVID-19. Any missing data at Week 16 that are not preceded by an intercurrent event will be imputed using multiple imputation as defined in Section 4.2.1.
4. Population-level summary measure=conditional odds ratio comparing bimekizumab to placebo adjusted for stratification factors used in the randomization.

The same imputation techniques and analysis model as in the primary efficacy analyses will then be used.

8.2.3.10 Cochran-Mantel-Haenszel test

The primary efficacy analyses from Section 8.2.2 will be repeated where the CMH test with fixed effects for treatment, Hurley stage at Baseline, and Baseline antibiotic use will be used as stratification variables. Pairwise treatment comparisons will be made based on the CMH test using the p-value for the general association. The odds ratio and associated confidence interval (CI) based on the Wald test will be provided.

8.2.3.11 Center-by-Treatment Interaction

The center-by-treatment interaction will be tested by adding center and a center-by-treatment interaction term in the logistic regression model described in Section 8.2.2. In the model, center will be based on the original centers prior to pooling. However, if the model is unable to converge due to a low number of participants at a given center, a pooling (see Section 3.7) will be described in order to allow the model to converge. In order to obtain reasonable estimates of variability for a treatment arm at a given center, a minimum of 21 participants will be considered acceptable for a center to be included in the model without pooling. Given the 2:2:2:1 randomization allocation scheme, this should provide a minimum of about 12 participants in the bimekizumab 320mg Q2W treatment group, 6 participants in the bimekizumab 320mg Q4W treatment group, and 3 participants in the placebo treatment group. Centers with fewer than 21 participants will be eligible for pooling. The pooling algorithm used is described in Section 3.7.

In order to achieve model convergence, other explanatory variables eg, Baseline Hurley Stage and Baseline antibiotic use may be dropped from the model. If model convergence is still not achieved, region and a region-by-treatment interaction term will be added to the model instead. Regions are defined in Section 3.7.

If the center-by-treatment interaction is not found to be significant ($\alpha=0.05$), then no further analyses will be performed. On the other hand, if the interaction is significant, further analyses

will be conducted to determine which center or centers may be the source of interaction. This will be done by running the logistic regression model (including the interaction term) where each center will be systematically removed from the model. This impact of a given center will be based on the change in the interaction p-value when that center is removed. The center or centers that appear to be driving the significant interaction effect will then be removed from the model to verify that conclusions remain the same with or without the influential center(s). This sensitivity analysis will be based on RS with MI/MCMC Monotone Regression for missing data.

8.3 Secondary efficacy endpoints

The secondary efficacy analyses will be performed based on the RS. Sensitivity analyses of the secondary endpoints will be performed on the CFS.

Missing data handling and sensitivity analyses of the secondary efficacy endpoints are described in Section 4.2.1.2.

The analyses of the secondary endpoints are summarized in Table 8–2 .

Table 8–2: Estimand Details and Attributes for Secondary Analyses

Estimands for Secondary Endpoints					
Objective Clinical Category	Statistical Category (Section)	Variable/Endpoint	Pop	IES	PLS (Analysis)
Secondary Objective: Evaluate the efficacy of bimekizumab on other measures of disease activity in study participants with moderate to severe HS					
HiSCR ₇₅	Secondary (Section 8.3.1)	HiSCR ₇₅ response at Week 16	RS	Composite strategy , as for the primary analysis.	The odds ratio versus placebo based on a logistic regression, as for the primary analysis.

Table 8–2: Estimand Details and Attributes for Secondary Analyses

Objective Clinical Category	Statistical Category (Section)	Estimands for Secondary Endpoints			
		Variable/Endpoint	Pop	IES	PLS (Analysis)
DLQI	Secondary (Section 8.3.2. 1)	Change from Baseline in DLQI total score to Week 16	RS	The main intercurrent events are receipt of systemic antibiotic rescue medication or discontinuation of study treatment due to an AE or lack of efficacy prior to Week 16. The intercurrent events will be handled using a hypothetical strategy , whereby all data at and after the intercurrent event will be treated as missing.	Difference in mean change from Baseline (LSMD from ANCOVA) to Week 16 in the DLQI total score for participants receiving bimekizumab versus placebo. Missing values will be imputed using MI – MCMC/Monotone Regression under a missing at random assumption.
DLQI	Secondary - Sensitivity (Section 8.3.2. 2)	Change from Baseline in DLQI total score to Week 16	RS	The main intercurrent events are receipt of systemic antibiotic rescue medication or discontinuation of study treatment due to an AE or lack of efficacy prior to Week 16. The intercurrent events will be handled using a while on treatment strategy , whereby only participants with a DLQI total score at Week 16 who have not had an intercurrent event on or before Week 16 are included.	Difference in mean change from Baseline (LSMD from ANCOVA) to Week 16 in the DLQI total score for participants receiving bimekizumab versus placebo. Missing values will not be imputed.

Table 8–2: Estimand Details and Attributes for Secondary Analyses

Objective Clinical Category	Statistical Category (Section)	Estimands for Secondary Endpoints			
		Variable/Endpoint	Pop	IES	PLS (Analysis)
HSSDD	Secondary (Section 8.3.3. 1)	Change from Baseline in worst skin pain score, as assessed by “worst skin pain” item in HSSDD to Week 16	RS	The main intercurrent events are receipt of systemic antibiotic rescue medication or discontinuation of study treatment due to an AE or lack of efficacy prior to Week 16. The intercurrent events will be handled using a hypothetical strategy , whereby all data at and after the intercurrent event will be treated as missing.	Difference in mean change from Baseline (LSMD from ANCOVA) to Week 16 in the worst skin pain score for participants receiving bimekizumab versus placebo. Missing values will be imputed using MI – MCMC/Monotone Regression under a missing at random assumption.
HSSDD	Secondary (Section 8.3.3. 2)	Change from Baseline in worst skin pain score, as assessed by “worst skin pain” item in HSSDD to Week 16	RS	The main intercurrent events are receipt of systemic antibiotic rescue medication or discontinuation of study treatment due to an AE or lack of efficacy prior to Week 16. The intercurrent events will be handled using a while on treatment strategy , whereby only participants with a HSSDD worst skin pain score at Week 16 who have not had an intercurrent event on or before Week 16 are included.	Difference in mean change from Baseline (LSMD from ANCOVA) to Week 16 in the worst skin pain score for participants receiving bimekizumab versus placebo. Missing values will not be imputed.

Table 8–2: Estimand Details and Attributes for Secondary Analyses

Objective Clinical Category	Statistical Category (Section)	Estimands for Secondary Endpoints			
		Variable/Endpoint	Pop	IES	PLS (Analysis)
HSSDD	Secondary (Section 8.3.4. 1)	Skin pain response at Week 16, as assessed by the “worst skin pain” item in the HSSDD, defined as an improvement in the weekly worst skin pain score of at least 3 points	RS ^a	Composite strategy , as for the primary analysis.	The odds ratio versus placebo based on a logistic regression, as for the primary analysis.
HSSDD	Secondary Sensitivity (Section 8.3.4. 2.1)	Skin pain response at Week 16, as assessed by the “worst skin pain” item in the HSSDD, defined as an improvement in the weekly worst skin pain score of at least 3 points	RS ^a	Composite strategy , as for the primary analysis where the occurrence of an intercurrent event will be handled by evaluating the corresponding participants as nonresponders.	The odds ratio versus placebo based on a logistic regression. Missing values for any other reason will also be imputed as nonresponders.

Table 8–2: Estimand Details and Attributes for Secondary Analyses

Estimands for Secondary Endpoints					
Objective Clinical Category	Statistical Category (Section)	Variable/Endpoint	Pop	IES	PLS (Analysis)
HSSDD	Secondary Sensitivity (Section 8.3.4.2.2)	Skin pain response at Week 16, as assessed by the “worst skin pain” item in the HSSDD, defined as an improvement in the weekly worst skin pain score of at least 3 points	RS ^a	The main intercurrent events are receipt of systemic antibiotic rescue medication or discontinuation of study treatment due to an AE or lack of efficacy prior to Week 16. The intercurrent events will be handled using a while on treatment strategy , whereby only participants with a HSSDD worst skin pain score at Week 16 who have not had an intercurrent event on or before Week 16 are included.	The odds ratio versus placebo is based on a logistic regression. Missing values will not be imputed.

AE=adverse event; ANCOVA=analysis of covariance; DLQI=Dermatology Life Quality Index; HiSCR=Hidradenitis Suppurativa Clinical Response; HSSDD=Hidradenitis Suppurativa Symptom Daily Diary; IES=intercurrent event(s) strategy; LSMD=Least Squares Mean Difference; MCMC=Markov Chain Monte Carlo; MI=multiple imputation; PLS=Population-level summary; Pop=Population; RS=Randomized Set

^a Analysis includes all study participants in the RS with a Baseline HSSDD Worst Skin Pain score of 3 or higher.

8.3.1 HiSCR₇₅ at Week 16

A categorical response variable, HiSCR₇₅ at Week 16 is defined to be equal to 1 if %ΔAN is less than or equal to -75%, and the change from Baseline in the abscess count is zero or negative (ie, non-positive) together with a non-positive change from Baseline in the draining tunnel (fistula/sinus tract) count, and 0 otherwise. This definition is introduced for identifying participants who respond to the treatment (1 = responder, 0 = nonresponder). The definition of percentage improvement from Baseline is given in Section 8.2.1.

For HiSCR₇₅ at Week 16, logistic regression as specified for the primary analysis will be implemented to test for superiority. The same analysis approach as outlined for the primary efficacy endpoint will be applied.

8.3.2 Change from Baseline in DLQI Total Score at Week 16

The DLQI is a questionnaire designed for use in adult participants with skin diseases and has been used in patients with HS. This is a validated, quality-of-life questionnaire that covers 6 domains including symptoms and feelings, daily activities, leisure, work and school, personal relationships, and treatment, as assessed over the past week.

The scoring of each answer for the DLQI is as follows:

Table 8–3: Dermatology Life Quality Index

DLQI Scoring	
Response	Score
Very much	3
A lot	2
A little	1
Not at all	0
Not relevant	0
Question unanswered	0
Q7: 'prevented work or studying' = yes	3

The DLQI total score is calculated by adding the score of each question. The maximum score is 30, and the minimum score is 0. The higher the score, the more quality of life is impaired.

Meaning of DLQI Total Score

0-1 = no effect at all on patient's life

2-5 = small effect on patient's life

6-10 = moderate effect on patient's life

11-20 = very large effect on patient's life

21-30 = extremely large effect on patient's life

This categorization will not be utilized in the analysis.

Because Q7 has a sub-question (referred to as Q7a here) after the leading yes/no question, some clarifying rules for scoring are provided:

- If Q7 is marked as "yes", a score of 3 is given regardless of the responses to Q7a.
- If Q7 is marked as "no", "not relevant", or is missing and Q7a is "A lot", a score of 2 is given.
- If Q7 is marked as "no", "not relevant", or is missing and Q7a is "A little", a score of 1 is given.
- If Q7 is marked as "no", "not relevant", or is missing and Q7a is "Not at all", a score of 0 is given.
- If Q7 is marked as "no" or "not relevant" and Q7a is missing, a score of 0 is given.
- If Q7 is missing and Q7a is missing, Q7 is considered unanswered (see below for details on how this impacts the DLQI total score).

If 1 question is left unanswered, this is scored 0 and the scores are summed and expressed as usual out of a maximum of 30. If 2 or more questions are left unanswered, the questionnaire is not scored.

Change from Baseline in DLQI total score is defined as Week 16 DLQI total score minus Baseline DLQI total score.

8.3.2.1 Primary analysis of change from Baseline in DLQI Total score at Week 16

Missing data imputation described in Section [4.2.1.2](#) will be applied.

Change from Baseline in DLQI total score will be presented by treatment group. The analysis model will be based on an ANCOVA with fixed effects of treatment, Hurley Stage at Baseline, Baseline antibiotic use and Baseline value as a covariate. The least square mean (LSM), standard error (SE), and 95% CI for the LSM will be presented by treatment group. For the comparison between placebo and bimekizumab: the difference between the LSM, the associated 97.5% CI for the contrasts, and the corresponding p-value will be presented. If one dose regimen is tested at the 0.05 significance level as determined in Section [4.5](#), then the confidence interval will be 95% instead of 97.5% for that dose with a corresponding $Z_{\alpha/2}$ of 1.96. Estimand and intercurrent event details are specified in [Table 8–2](#).

8.3.2.2 Sensitivity analysis of change from Baseline in DLQI Total score at Week 16

A sensitivity analysis using the same analysis model as in Section [8.3.2.1](#) will be used, based on observed data. Estimand and intercurrent event details are specified in [Table 8–2](#).

8.3.3 Change from Baseline in Skin Pain score at Week 16, as assessed by the “worst skin pain” item in the HSSDD

The items on the HSSDD assess patients' perception of the core symptoms of HS experienced in the past 24 hours: pain, smell or odor, drainage or oozing from HS lesions, and itch on an 11-point numeric rating scale (NRS). Two items assess skin pain: worst skin pain and average skin pain.

Weekly averages will be derived for each of the items of the HSSDD for weeks matching the post-Baseline dosing weeks up to Week 16. A weekly average is the sum of the scored item over the course of the study week divided by the number of days on which the item was completed. The weekly averages will be relative to the respective visit date except for Baseline, which will be anchored to the first dose of study drug. A weekly average will only be calculated if at least 4 non-missing values (not necessarily consecutive) are available. Otherwise, the HSSDD weekly average for the given question will be set to missing.

Baseline will be computed as the average from the first 7 consecutive day period in which there are at least 4 non-missing entries. That is, first consider the first 7 consecutive days prior to the Baseline visit, but not including the Baseline visit day itself. If there are at least 4 non-missing values (not necessarily consecutive), then the Baseline average will be calculated. If there are less than 4 values, the 7 consecutive day period will move one day earlier. If there are at least 4 non-missing values (not necessarily consecutive) in that period, then the Baseline average will be calculated. This will continue until there are at least 4 non-missing values in a 7 consecutive day

period in the 14 days prior to Baseline. If there is no period in which there are at least 4 non-missing entries, then the Baseline value will be set to missing.

Change from Baseline in worst skin pain score is defined as the average Week 16 worst skin pain score minus the Baseline worst skin pain score. Missing data imputation described in Section 4.2.1.2 will be applied to the weekly averages and not to the individual daily PRO data.

8.3.3.1 Primary analysis of change from Baseline in skin pain score at Week 16

Change from Baseline in worst skin pain score will be presented by treatment group. The analysis model will be based on an ANCOVA with fixed effects of treatment, Hurley Stage at Baseline, Baseline antibiotic use, analgesic use (Section 6.4.2) and Baseline value as a covariate.

The LSM, SE, and 95% CI for the LSM will be presented by treatment group. For the comparison between placebo and bimekizumab, the difference between the LSM, the associated 97.5% CI for the contrasts, and the corresponding p-value will be presented. If one dose regimen is tested at the 0.05 significance level as determined in Section 4.5, then the confidence interval will be 95% instead of 97.5% for that dose with a corresponding $Z_{\alpha/2}$ of 1.96.

8.3.3.2 Sensitivity analysis of change from Baseline in skin pain score at Week 16

A sensitivity analysis using the same analysis model as in Section 8.3.3.1 will be used, based on observed data. Estimand and intercurrent event details are specified in Table 8–2.

8.3.4 HSSDD skin pain response at Week 16

The analysis set for the analyses of the skin pain response will be restricted to those study participants in the RS with a Baseline worst skin pain score of 3 or higher. The weekly scores and Baseline score are derived as specified in Section 8.3.3.

8.3.4.1 Primary analysis of skin pain response at Week 16

Skin pain response at Week 16, as assessed by the “worst skin pain” item in the HSSDD, is defined as an improvement in the weekly worst skin pain score of at least 3 points versus Baseline.

The primary analysis will be based on a logistic regression model including a fixed effect for treatment, Hurley stage at Baseline, Baseline antibiotic use, and analgesic use (Section 6.4.2).

The odds ratio versus placebo, p-value (from Wald test), and 97.5% CI will be calculated. If one dose regimen is tested at the 0.05 significance level as determined in Section 4.5, then the confidence interval will be 95% instead of 97.5% for that dose. Missing data will be handled as specified in Section 4.2.1.2. Estimand and intercurrent event details are specified in Table 8–2.

The number and percentage of participants who are pain responders at Week 16 will be summarized by treatment group.

By-participant listings of pain response status will be provided.

8.3.4.2 Sensitivity analyses of Skin Pain Response at Week 16

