2.4 Determination of sample size

A total of 490 study participants will be randomly assigned in a 2:2:2:1 ratio (stratified by Hurley Stage and current antibiotic use) to the following treatment arms:

- Bimekizumab 320mg Q2W during Initial Treatment Period (Weeks 0-16) and Maintenance Treatment (Weeks 16-48) Period, N=140
- Bimekizumab 320mg Q2W during Initial Treatment Period (Weeks 0-16), and Bimekizumab 320mg Q4W during Maintenance Treatment Period (Weeks 16-48), N=140
- Bimekizumab 320mg Q4W during Initial Treatment (Weeks 0-16) and Maintenance Treatment Periods (Weeks 16-48), N=140
- Placebo during Initial Treatment Period (Weeks 0-16), and Bimekizumab 320mg Q2W during Maintenance Treatment Period (Weeks 16-48), N=70

The analysis of the primary efficacy endpoint and secondary efficacy endpoints are based on a comparison of bimekizumab versus placebo at Week 16, with alpha adjustment strategy as indicated in Section 4.5.

The power to detect a statistically significant difference for each of the endpoints are shown in Table 2-1. Notably, with a 2-sided significance level of 0.025, the sample size of 140:70 provides 73% power for detecting at least a difference of 1.5 (bimekizumab Q4W vs placebo) for the Worst Skin Pain change from Baseline (CFB) endpoint.

Given the high level of power for each of the primary and key secondary endpoints at the 0.025 significance level for the Q2W comparison (power ≥ 0.89), and per the alpha spending strategy, there is a high likelihood that the Q4W comparison of Worst Skin Pain CFB vs placebo will be allowed to be tested against the 0.05 level of significance. The power for this latter test is 81%. The sample size is thus ultimately driven by the Worst Skin Pain CFB endpoint. Furthermore, the randomization ratio of 2:2:2:1 has been chosen to provide study participants with a high probability (6/7 ~ 86%) of being randomized to active study drug.

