After randomization for this study was complete, an additional endpoint to assess Worst Skin Pain response was included in the sequential testing procedure. This additional endpoint is based on the threshold for clinically meaningful change and is defined as at least a 3 point decrease from Baseline in HSSDD weekly worst skin pain score at Week 16 among study participants with a score of ≥ 3 at Baseline. Note that the power calculations reported in Table 2-1 for this endpoint are based on the sample size that was initially driven by the Worst Pain CFB endpoint as described above. With a 2-sided significance level of 0.025, the sample size of 104:52 in the subset of participants reporting Baseline HSSDD worst skin pain score at or beyond the threshold for clinically meaningful change (ie, Baseline HSSDD ≥ 3) provides 53% power for

detecting a statistically significant difference between bimekizumab Q4W and placebo in the proportion of Worst Pain responders.

Note that the power at the 0.025 level of significance associated with this endpoint for the comparison between bimekizumab Q2W and placebo is 95%. The Q4W comparison of Worst Skin Pain response vs placebo against the 0.05 level of significance is therefore likely, and the power at this significance level is 65%. Given the strength of the power for the bimekizumab Q2W arm vs placebo across endpoints, it is considered acceptable to have a relatively low power for this final endpoint in the testing sequence for the bimekizumab Q4W treatment arm vs placebo.

Table 2-1: Power calculation assumptions and methods

Endpoint	Power $\alpha = 0.025$, 2-sided		Assumptions		
	Q2W	Q4W	Week 16 Bimekizumab Q2W N=280 ^a	Week 16 Bimekizumab Q4W N=140	Week 16 Placebo N=70
HiSCR ₅₀	0.99	0.90	Proportion responders=0.60	Proportion responders=0.50	Proportion responders=0.25
HiSCR ₇₅	0.99	0.98	Proportion responders=0.45	Proportion responders=0.35	Proportion responders=0.10
DLQI	0.99	0.96	Mean CFB=-5.4; SD=6.8	Mean CFB=-4.8; SD=6.8	Mean CFB=-0.8; SD=6.6
Worst Skin Pain CFB ^b	0.89	0.73	Mean CFB=-2.2; SD=3.2	Mean CFB=-2.0; SD=3.2	Mean CFB=-0.5; SD=3.7
Worst Skin Pain Response ^c	0.95	0.53	Proportion responders=0.53	Proportion responders=0.43	Proportion responders=0.23

CFB=change from Baseline; Q2W=every 2 weeks; Q4W=every 4 weeks; SD=standard deviation

Note: Estimates for HS0003 are based on Week 12 data from the HS0001 study.

^a Pooled Q2W at Week 16 from Q2W/Q2W and Q2W/Q4W arms

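### Worst skin pain is planned with a larger SD in the small placebo arm but analysed with one common residual variance, so if that SD ratio holds the standard errors are too small and the printed powers belong to another test

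*SAP*

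**What the plan says.** SAP 2.4 (Table 2-1) gives these planning values for worst skin pain change from Baseline: "Mean CFB=-2.2; SD=3.2" for Q2W, "Mean CFB=-2.0; SD=3.2" for Q4W and "Mean CFB=-0.5; SD=3.7" for placebo. The group sizes are 280, 140 and 70. The 280 is footnoted "Pooled Q2W at Week 16 from Q2W/Q2W and Q2W/Q4W arms", so Q2W to placebo is 4:1. The printed powers at two-sided 0.025 are 0.89 (Q2W) and 0.73 (Q4W). The text repeats the second: "with a 2-sided significance level of 0.025, the sample size of 140:70 provides 73% power". It adds 81% for Q4W if that dose can be tested at 0.05. No test is named for these calculations.

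SAP 8.3.3.1 defines the confirmatory analysis: "The analysis model will be based on an ANCOVA with fixed effects of treatment, Hurley Stage at Baseline", plus Baseline antibiotic use, analgesic use and the Baseline score. The p-value and the 97.5% CI (95% where the dose is tested at 0.05) come from the least-squares-mean contrast with placebo. Sections 4.1, 4.2.2.1 and 8.3.3.1 provide for neither a group-specific residual variance nor a robust standard error. Section 8.3.3.2 applies the same model to observed data.

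**The concern.** The smallest arm is planned with the largest SD. A common residual variance is dominated by the 420 bimekizumab participants, so it understates the uncertainty of every difference from placebo. The confidence interval is then too narrow and the test too liberal. The printed powers also appear to describe a different test from the one that will be run.

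The endpoint matters because it is Step 4 of the multiplicity-controlled sequence in 4.5, and 2.4 says it ultimately drives the sample size. The observed-case analysis shares the model, so it cannot expose the problem. Imputing separately by arm and combining by Rubin's rules does not correct the standard error computed within each imputed data set.

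**Working it through.** **Inputs (Table 2-1).** N = 280 / 140 / 70 and SD = 3.2 / 3.2 / 3.7 for Q2W / Q4W / placebo. Differences from placebo: 2.2 − 0.5 = 1.7 (Q2W) and 2.0 − 0.5 = 1.5 (Q4W).

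**Step 1: reproduce the printed power.** With unequal variances, SE = √(s₁²/n₁ + s₂²/n₂).

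- Q2W: √(10.24/280 + 13.69/70) = √0.2321 = 0.482. Noncentrality 1.7/0.482 = 3.53, Satterthwaite df 96.4.
- Q4W: √(10.24/140 + 13.69/70) = √0.2687 = 0.518. Noncentrality 1.5/0.518 = 2.89, df 121.8.

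| Calculation | Q2W, 0.025 | Q4W, 0.025 | Q4W, 0.05 |
|---|---|---|---|
| Printed | 0.89 | 0.73 | 0.81 |
| Unequal-variance t | 0.893 | 0.733 | 0.819 |
| Unpooled normal approximation | 0.901 | 0.743 | 0.825 |
| Pooled t, df-weighted SD | 0.945 | 0.782 | 0.856 |
| Pooled t, root-mean-square SD 3.46 | 0.923 | 0.759 | 0.839 |
| Pooled t, SD 3.7 in both arms | 0.882 | 0.695 | 0.787 |

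Only the two unequal-variance versions stay within two points of all three printed figures, and the t version is the closer.

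**Step 2: standard error of the model as written.** With all three groups in one model, the residual SD is √((418 × 3.2² + 69 × 3.7²)/487) = √(5224.93/487) = 3.28.

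- Q2W: model SE = 3.28 × √(1/280 + 1/70) = 0.438, against a true SE of 0.482. Ratio 0.908, about 9% too small.
- Q4W: model SE = 3.28 × √(1/140 + 1/70) = 0.479, against 0.518. Ratio 0.925, 7.5% too small.

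**Step 3: consequence.** The two-sided rejection rate with equal means is 2 × (1 − Φ(z × ratio)). Coverage is one minus that rate.

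- Nominal 2.5% (z = 2.24): Q2W 4.2%, Q4W 3.8%. The 97.5% CI covers about 95.8% and 96.2%.
- Nominal 5% (z = 1.96): Q2W 7.5%, Q4W 7.0%.

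A simulation of 400,000 trials gave 4.17% and 3.87% at nominal 2.5%, and 7.5% and 7.0% at nominal 5%. The unequal-variance test for Q2W gave 2.51% and 5.01%. Simulated power of the common-variance test at the planned effects is about 0.93 (Q2W) and 0.79 (Q4W) at 0.025, and about 0.86 (Q4W) at 0.05.

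**Step 4: dependence on assumptions (nominal 2.5%, Q2W unless stated).**

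- Active SD 3.2 with placebo SD 2.8, 3.2, 3.4, 3.7, 4.0: 1.5%, 2.5%, 3.1%, 4.2%, 5.3%. At a ratio of 1.08 the rate is about 3.3%.
- Covariates shrink all SDs in proportion: 4.2%, unchanged.
- Covariates remove the same absolute variance in each arm (assumed 10% to 50% of 3.2²): 4.4% to 5.9%.
- Each dose fitted with placebo only: 4.0% (Q2W) and 3.3% (Q4W).
- A simulated ANCOVA with one continuous and one binary covariate (10,000 trials per setting) gave 4.3% with uninformative covariates and 4.7% when they removed 30% of 3.2² in every arm. HC3 standard errors gave 2.6% and 2.5%.

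**The case against.** **The SDs belong to the alternative.** They sit in a row that assumes treatment effects. A drug with no effect at all would leave all arms with one distribution, and the test would then hold its 2.5%. This stands. The 4.2% needs equal means with unequal SDs. The coverage shortfall does not, because it applies at the planned effects too.

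**The ratio is uncertain.** The values come from Week 12 data of an earlier study and are SDs of raw change, not of ANCOVA residuals. This stands, and the sign could reverse: if placebo is less variable, the test is conservative.

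**The power method is inferred.** The SAP names none, and 0.819 reaches 81% only by truncation. This also stands. The pooled versions nevertheless miss, by up to about five points.

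**The mismatch does no harm to the sample size.** This is correct. The printed powers are lower than those of the test as written, so nothing here suggests too few participants.

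**Common-variance ANCOVA is standard, and the figures are for complete data.** Both are true. Multiple imputation was not simulated, but it does not repair the standard error within each imputed data set.

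A reader might infer that the trial's overall type I error is inflated to 4.2%. The documents do not support that. Under 4.5 this test is reached for a dose only after HiSCR50, HiSCR75 and DLQI succeed for that dose, so the figure is local to Step 4 and conditional on the SD ratio.

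**Conclusion.** The point holds conditionally. Given the SAP's planning SDs and allocation, and assuming that the ratio 3.7/3.2 = 1.16 carries over to the residuals, the ANCOVA in 8.3.3.1 understates the standard error against placebo for both doses. The intervals fall 1.7 points (Q2W) and 1.3 points (Q4W) short of 97.5% coverage. The local rejection rate exceeds its nominal level when means are equal but SDs differ, and the excess disappears when the SDs are equal. The printed powers fit an unequal-variance test rather than the one specified.

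It may be tempting to extend this to DLQI. Its planning SDs (6.8 in the bimekizumab groups, 6.6 in placebo) are nearly equal, so 8.3.2.1 is not materially affected.

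**What to change.** In 8.3.3.1, and in the matching observed-case analysis in 8.3.3.2, allow a separate residual variance per treatment group with Satterthwaite or Kenward-Roger degrees of freedom, or use HC3 robust standard errors. In 8.3.3.1 do this in each imputed data set and combine by Rubin's rules. Base the p-value and the 97.5% or 95% CI on that standard error. Name in 2.4 the test behind the printed powers.

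The cost is one sentence and one model option. Power drops from about 0.93 (Q2W) and 0.79 (Q4W) at 0.025 to the printed 0.89 and 0.73, and for Q4W at 0.05 from about 0.86 to about the printed 81%. No extra participants are needed.
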